System (IADS [20]; $n = 64$ sounds), from freely available sound databases (<https://www.fesliyanstudios.com/royalty-free-sound-effects-download>; $n = 12$ sounds), as well as from published literature [5] ($n = 25$ sounds). The IADS is a standardized set of .wav files that have been normed for arousal and valence levels. Non-misophonic aversive and neutral stimuli for this task were selected using the standardized values of valence and arousal from the IADS. Misophonic sounds were selected using the literature, to include sounds that have been previously described as being particularly triggering for misophonic individuals. To make sounds from various sources consistent, each sound was cut or repeated so that the amount of time the sound would play was 6 s. Each sound was followed by rating screens and a 6 s return to baseline period. All participants were asked to rate after each sound whether it was a positive, neutral, or negative sound and the intensity of their (positive/negative) arousal when listening to the sound. In addition, participants in the misophonia group alone were asked whether the aversive sound was a misophonic trigger for them (yes/no).

Based on this task, for each participant, a personalized set of sounds was selected for the neurostimulation and for the neuroimaging sessions. For the misophonia group, the highest negative arousal sounds that were flagged as misophonic triggers were included in the misophonic sounds condition. The highest negative arousal sounds that were not marked as misophonic triggers were included in the aversive condition. Sounds marked as neutral were randomly sampled for the neutral condition. For the control group, highest negative arousal sounds that were initially labeled as potentially misophonia related created the misophonic sounds, the highest negative arousal sounds that were from either the original aversive or neutral groups were selected for the aversive condition, and a random sampling of neutral sounds was selected for the neutral stimuli condition.

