If there were too many high arousal sounds, a randomizer was employed to select the stimuli. If there were too few sounds, the stimulus set could have the same sound repeating twice (repeating sounds being selected at random). For the experimental sessions, 12 of each misophonic, aversive, and neutral sounds were selected. These sounds were shuffled so they would play in different orders during the imaging and during the neurostimulation sessions. Sounds repeated during the neurostimulation session, once for each run (i.e., the same sounds were played during different neurostimulation conditions, but in different order). One participant did the task twice because their answers failed to record the first time. Another participant came too late to do their sound task, could not be rescheduled, and as a result, another participant's personalized stimulus set (from the same group) was used to run them through the experimental sessions.

5. Neuroimaging sessions

MRI training:

Participants completed an imaging session as soon as possible after the eligibility intake. During the first hour of this session, participants were introduced to the task stimuli and were trained in how to respond accordingly: simply look at the screen when a cross was presented (passive baseline); indicate with a button press the direction of an arrow showed on the screen (active baseline); prepare to downregulate emotions associated with the sounds they hear when seeing a downward arrow; and prepare to throw themselves into listening and allowing any experience that arises during a sound file when seeing a wave symbol on the screen (~).

Participants were then introduced to CR as a strategy to use when instructed to downregulate emotions. Participants were taught to think that sounds were not real (e.g., a movie sound effect), or that the context meant something less negative (e.g., someone is about to pick up a baby that is crying). Participants practiced these strategies on two standardized sounds. Strategies were briefly covered for the participant to be able to engage in the targeted behavior during the scan, but not such that the participant learned new ways to downregulate emotions.

MRI acquisition:

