The experimental session (Figure 2C) included a 180s pre- session baseline, followed by three experimental runs, one using HF-rTMS over the right DLPFC (39 trains), one using continuous LF-rTMS over the right mPFC, and one using sham rTMS applied over one of those two targets, in a randomized order. Each run included a pre-task baseline (180s), a habituation period (180s) where neurostimulation was administered while the participant was not given any instruction, a sound task, including 5 blocks (600s), and a 600s break. Neurostimulation was administered throughout the sound task. Each block (120s long) started with an instruction (downregulate or listen) and was followed by four sounds played on repeat for 25 seconds (either misophonic, neutral, or aversive depending on the block). Sound and block order was randomized within each run. During the sound presentation a downward arrow (for downregulate), or wave symbol (~, for listen) was present on the screen to guide participants on what to do, neurostimulation and psychophysiological data collection was ongoing.

Psychophysiological Data

HR and GSR were recorded during the whole duration of the sound task and the neurostimulation session. AcqKnowledge software was used to collect and pre-process raw ECG data by using a built in automated heart rate variability (HRV) analysis tool that follows established frequency domain algorithm guidelines [75]. For each baseline, habituation, and 120s listen or down-regulate block, high frequency HRV (HF-HRV) was extracted to capture emotion regulation. Reactivity to emotional cues was captured through GSR. For each baseline, habituation period, and for each sound presentation we extracted the maximum GSR value as a measure of peak emotional arousal. We then removed from the GSR signal, with the help of a MATLAB program, skin conductance responses (SCRs) by leveling the signal when clear spikes were identified [76]. In this way, the tonic signal, or skin conductance level (SCL), was also extracted from each baseline, habituation to rTMS, and 120s listen/regulate block. SCL values represent average arousal during these distinct time periods.

7. Statistical Analyses

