To compare the effects our neurostimulation conditions, we conducted four analyses examining SUDS, peak GSR (SCR; peak arousal), SCL (tonic arousal), and HF-HRV. For the SUDS analyses, we examined the difference between SUDS at the end of each sound and the baseline SUDS collected after the task baseline. If task baseline SUDS were missing, session baseline SUDS were utilized instead. For the SCR analysis, the maximum value of the GSR during the presentation of each sound was used as outcome. For those two variables, the experimental group was used as a between-subject variable (misophonic or emotion dysregulation), and the experimental neurostimulation condition (active HF-rTMS over the right DLPFC, active LF-rTMS over the mPFC- insula, sham rTMS), the block instruction (downregulate misophonic, downregulate aversive, hear misophonic, hear aversive, hear neutral), the order effect of the 3 neurostimulation condition time within the task (0-2, corresponding with the runs employed), within the run (0-4, corresponding to each block), and within the block (0-3, corresponding to each of the sounds played), were used a within-subject variable. The experimental group by neurostimulation condition by block instruction interactions were entered as effects in the SUDS and SCR analyses. For SCR, the maximum GSR value during the habituation period was also controlled for. For the SCL and HF-HRV analyses, the experimental group and neurostimulation condition, and block instruction were also used but only the average within each block was used as outcome, time within block was excluded because HF-HRV requires at least 120s to be accurately assessed, and baseline values were added as main effects, time was considered a categorical variable. To account for multiple comparisons, we used a Bonferroni correction, and dropped the significance threshold to .0125. Differences between LF and HF rTMS were not hypothesized, but explored where both stimulation conditions were different than sham.

Planned covariates for all analyses included coil-to-cortex distance- given evidence that higher distance may impede the effectiveness of neurostimulation interventions for emotion regulation that are not designed to account for this parameter [77,78] - and data-driven covariates were also examined and added to these analyses as needed. Effect sizes were computed by using Feingold's formula [79] and interpreted using Cohen's specifications [80].

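### The SUDS and peak-GSR models name sound position but not sound identity, so sound-type tests may be too liberal; active-versus-sham tests are not, but may lose some precision

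*Combined protocol and SAP*

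**What the plan says.** Section 4 (Sound Task) states that "for each participant, a personalized set of sounds was selected for the neurostimulation and for the neuroimaging sessions". For the experimental sessions "12 of each misophonic, aversive, and neutral sounds were selected", and if too few qualified, "the stimulus set could have the same sound repeating twice". The sounds recur once per run in the neurostimulation session: "the same sounds were played during different neurostimulation conditions, but in different order".

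Section 6 (TMS experiment) gives three runs, each with five blocks of 120 s. A block opens with an instruction, "followed by four sounds played on repeat for 25 seconds". It adds: "Sound and block order was randomized within each run".

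Section 7 (Statistical Analyses) models SUDS change and peak GSR at the level of the single sound. The named terms are group, stimulation condition, block instruction, run order (0-2), block order (0-4) and position "within the block (0-3, corresponding to each of the sounds played), were used a within-subject variable". The group by stimulation by block-instruction interactions are entered, and the threshold for the four analyses is .0125. The section leaves the covariance structure to an unspecified analytic choice and does not list the random effects. No fixed or random term for the sound itself appears.

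**The concern.** Each participant supplies 3 runs × 5 blocks × 4 sounds = 60 records per outcome, but these come from a much smaller set of distinct sounds. Three plays of one sound to one participant should be more alike than plays of three different sounds. The model needs to know this, and position does not tell it: position 2 in run 1 and position 2 in run 3 will generally be different sounds.

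The consequence depends on the contrast. Misophonic versus aversive, and its interaction with group, compares different sounds, so treating replays as new sounds overstates the information. Active versus sham compares the same sounds with themselves. Sound-to-sound variation should then largely cancel, yet the model leaves it in the residual.

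GSR change is a primary outcome and SUDS a secondary one. Sound type is among the planned comparisons in the sample-size paragraph, and marginal means are compared after significant effects.

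**Working it through.** **The plan's own figure.** Four analyses at overall .05 give .05/4 = .0125, as stated. Two-sided testing is assumed, with critical value z = 2.498.

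**Inputs from the documents.** Per run there are 2 misophonic, 2 aversive and 1 neutral block of 4 sounds: 8 + 8 + 4 = 20 slots. Over three runs that is 24 misophonic and 24 aversive records per participant.

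**Inputs assumed (not in the documents).** Shares of record variance are: between-sound within participant *s* = 0.2, 0.3 or 0.4; participant-by-run *r* = 0.1; residual *e* = 0.7, 0.6 or 0.5. The same 8 misophonic and 8 aversive sounds recur in each run. The variances below are per participant; the number of participants cancels from the ratios.

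**1. Misophonic versus aversive, no contrast-specific participant variance fitted**

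- Model variance: 2(*s*+*e*)/24 = 2(0.9)/24 = 0.075 in all three cases.
- True variance: 2(*s*/8 + *e*/24) = 0.108, 0.125, 0.142.
- Model SE / true SE: 0.832, 0.775, 0.728, so the SE is 17%, 23% or 27% too small.
- Real rejection rate, 2[1 − Φ(2.498 × ratio)]: 3.8%, 5.3%, 6.9%.

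The same ratio applies to group by sound type. With *s* = 0.05 and *e* = 0.85 the true variance is 0.083, the ratio 0.949 and the rejection rate 1.8%, so the effect fades as *s* falls.

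**2. Simulation of how sounds fill the slots**

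The setting was 54 participants, 4,000 replicates, a participant-intercept model, and hear-misophonic versus hear-neutral. Sound variance was 0.25, 0.5 or 1 times residual variance.

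| Allocation of sounds | Rejection rate at nominal .0125 |
|---|---|
| Same sounds, same block type each run | .037, .053, .078 |
| Same sounds, moving between listen and downregulate blocks | .031, .043, .063 |
| Redrawn from the 12 each run | .023, .027, .035 |

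If each contrast instead has its own participant-level variance, the rate is .011 to .017 across these scenarios, which is near nominal. That protection is lost if sounds also have effects shared across participants. With sound variance 0.25 plus shared variance 0.1 (residual = 1), the rate is .07 to .09, against .12 to .14 for the intercept-only model.

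**3. Active versus sham, participant-by-run variance estimated from the data**

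When the same sounds recur, run means do not vary because of sound. The estimated run variance therefore settles at about *r* − *s*/20.

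- *Main effect over 20 sounds.* Model: 2(*r* − *s*/20 + (*s*+*e*)/20) = 2(*r* + *e*/20), which equals the true variance. The SE is about right.
- *One block type, same four sounds each run.* Model: 2(*r* − *s*/20 + (*s*+*e*)/4) = 0.63, 0.62, 0.61. True: 2(*r* + *e*/4) = 0.55, 0.50, 0.45. SE ratio: 1.07, 1.11, 1.16.

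Holding *r* at 0.1 in the model formula gives 0.65 throughout and ratios of 1.09, 1.14 and 1.20. That overstates the excess, because a fitted model would not keep *r* fixed.

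**The case against.** A reader might infer that the standard errors are wrong for both kinds of contrast. The documents do not support that.

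- **The random effects are not listed.** If participant variances by block instruction were fitted, the sound-type test is close to nominal without any sound term. This stands, except for sound effects shared across participants. Such effects are plausible because all personal sets are drawn from one pool of 101 sounds.
- **Stimulation comparisons are the stated purpose of these models.** Sound is crossed with stimulation, so sound effects largely cancel, including in stimulation-by-sound-type contrasts. A reader who infers false-positive inflation for active versus sham would be mistaken: replaying sounds produces none. This stands in full.
- **The a priori misophonic-versus-aversive outcomes are BOLD contrasts,** which these models do not analyse. This also stands. The exposure is confined to the block-instruction and group-by-block effects on SUDS and peak GSR.
- **The slot count is unclear.** Three types × 12 sounds = 36 do not fit 20 slots per run, so not every selected sound can be heard in every run. The documents do not say which sounds are used, or whether a sound keeps its instruction across runs. Redrawing lowers the inflation but does not remove it.
- **The variance shares have no source in the documents.** Choosing the highest-arousal sounds within type may narrow between-sound variation. This is fair, and it limits what can be said about size.

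**Conclusion.** The gap is real: sounds are replayed in a new order, and none of the named terms can link the replays. What follows is conditional. Without contrast-specific participant variances, sound-type and group-by-sound-type tests of SUDS and peak GSR are too liberal. The rate is about 4% to 7% at a nominal .0125 if the same 8 sounds per type recur and between-sound shares are 0.2 to 0.4, and about 2% to 3.5% in the scenarios where sounds are redrawn. With such variances fitted, only sound effects shared across participants remain unaccounted for.

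Active-versus-sham inference is not threatened. With a participant-by-run variance estimated, the main effect is about right, and contrasts within one block type have standard errors at most about 7% to 16% too large, which costs precision and not validity. All these sizes rest on assumed variance shares and go to zero with between-sound variance.

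**What to change.** Add a participant-by-sound random intercept (sound file within participant) to the SUDS and peak-GSR models, and a crossed sound-file intercept if the model converges. A sound placed twice in one participant's set should keep a single identity.

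State in Statistical Analyses which random effects were fitted. State also how 12 sounds per type fill the 4 neutral, 8 misophonic and 8 aversive slots in each run, and whether a sound keeps its instruction across runs.

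The cost is one or two extra variance components, a sound identifier taken from the playback record, a refit of two models, and possibly slower convergence. In return, the sound-type tests gain protection and the within-block active-versus-sham intervals may tighten.

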The experimental session (Figure 2C) included a 180s pre- session baseline, followed by three experimental runs, one using HF-rTMS over the right DLPFC (39 trains), one using continuous LF-rTMS over the right mPFC, and one using sham rTMS applied over one of those two targets, in a randomized order. Each run included a pre-task baseline (180s), a habituation period (180s) where neurostimulation was administered while the participant was not given any instruction, a sound task, including 5 blocks (600s), and a 600s break. Neurostimulation was administered throughout the sound task. Each block (120s long) started with an instruction (downregulate or listen) and was followed by four sounds played on repeat for 25 seconds (either misophonic, neutral, or aversive depending on the block). Sound and block order was randomized within each run. During the sound presentation a downward arrow (for downregulate), or wave symbol (~, for listen) was present on the screen to guide participants on what to do, neurostimulation and psychophysiological data collection was ongoing.

Psychophysiological Data

HR and GSR were recorded during the whole duration of the sound task and the neurostimulation session. AcqKnowledge software was used to collect and pre-process raw ECG data by using a built in automated heart rate variability (HRV) analysis tool that follows established frequency domain algorithm guidelines [75]. For each baseline, habituation, and 120s listen or down-regulate block, high frequency HRV (HF-HRV) was extracted to capture emotion regulation. Reactivity to emotional cues was captured through GSR. For each baseline, habituation period, and for each sound presentation we extracted the maximum GSR value as a measure of peak emotional arousal. We then removed from the GSR signal, with the help of a MATLAB program, skin conductance responses (SCRs) by leveling the signal when clear spikes were identified [76]. In this way, the tonic signal, or skin conductance level (SCL), was also extracted from each baseline, habituation to rTMS, and 120s listen/regulate block. SCL values represent average arousal during these distinct time periods.

7. Statistical Analyses

Preliminary analyses, including *t*-tests and chi-squares, were conducted to assess demographic differences between experimental groups. We also examined any differences on matching variable (sex at birth, age) and other potential confounding variables like demographic characteristics, use of medication, dissociation during the experimental task, sleepiness during the experimental day, discomfort during neurostimulation, or psychophysiological effects induced by rTMS alone.

Primary outcomes set *a priori* were BOLD signal differences within the dlPFC and vmPFC during regulation of misophonic versus aversive sounds, BOLD signal differences within the AIC when listening to misophonic versus aversive sounds, change in HF-HRV and GSR during experimental blocks from baseline, acceptability of procedures as measured by percent of participants who complete the sessions. Secondary outcomes included self-reports (SUDS during the neurostimulation experiment, DERS, PROMIS-43), whole-brain BOLD changes when comparing aversive with neutral sound presentation and regulation, and when comparing misophonic with neutral sounds presentation and regulation.

To examine differences in functional activation between groups during the neuroimaging experiment, a group analysis was performed. Each functional and PPI FSL Level 2 analysis for each participant was entered into a third level FSL FEAT analysis assessing the differences between participants who in either the misophonia or the clinical control group.

To compare groups on functional connectivity during contrasts that were not included for targeting, four additional whole brain PPI analyses were performed using the same left insula seed, thresholded at 2.3, and then using the time series from this anatomical mask as the physiological regressor. In addition to the functional task regressors, each additional PPI analysis included one of the contrasts of interest as

regressors: [listen to misophonic vs. aversive sounds], [downregulate vs. listen to misophonic sounds], [listen to aversive vs. neutral sounds], and [downregulate vs. listen to aversive sounds]. For all, the PPI was defined as the interaction between this event and the physiological regressor (66, 67). This method was performed for each subject and for each run. A third level analysis was then performed to assess the differences between groups. PPI analyses probe the synchronization of brain activity between two brain regions allowing us to differentiate regions which interact with each other versus work independently during experimental tasks (68). Whole brain Z image statistics (from both functional and PPI analyses) were thresholded using clusters determined by $Z > 2.3$ and a corrected cluster significance of $p = .05$ (69). Mixed-effects hierarchical linear models (MMANOVA) with analytically determined covariance structures were used to analyze the repeated measures data (70). All MMANOVA models used a restricted estimated maximum likelihood model to account for missing data (71) (i.e., cases with missing data were not discarded, but slopes for each participant were computed with the data available). Estimated marginal means (EMMs) were compared using LSD corrections for significant main and interaction effects, and are presented in the results section. For data that was not repeated, independent sample t -tests or non-parametric equivalents were employed. To test the neurobiological basis of misophonia, correlation analyses with neuroimaging data extracted from regions of interest (ROIs) and baseline behavioral measures were employed.

To compare the effects our neurostimulation conditions, we conducted four analyses examining SUDS, peak GSR (SCR; peak arousal), SCL (tonic arousal), and HF-HRV. For the SUDS analyses, we examined the difference between SUDS at the end of each sound and the baseline SUDS collected after the task baseline. If task baseline SUDS were missing, session baseline SUDS were utilized instead. For the SCR analysis, the maximum value of the GSR during the presentation of each sound was used as outcome. For those two variables, the experimental group was used as a between-subject variable (misophonic or emotion dysregulation), and the experimental neurostimulation condition (active HF-rTMS over the right DLPFC, active LF-rTMS over the mPFC- insula, sham rTMS), the block instruction (downregulate misophonic, downregulate aversive, hear misophonic, hear aversive, hear neutral), the order effect of the 3 neurostimulation condition time within the task (0-2, corresponding with the runs employed), within the run (0-4, corresponding to each block), and within the block (0-3, corresponding to each of the sounds played), were used a within-subject variable. The experimental group by neurostimulation condition by block instruction interactions were entered as effects in the SUDS and SCR analyses. For SCR, the maximum GSR value during the habituation period was also controlled for. For the SCL and HF-HRV analyses, the experimental group and neurostimulation condition, and block instruction were also used but only the average within each block was used as outcome, time within block was excluded because HF-HRV requires at least 120s to be accurately assessed, and baseline values were added as main effects, time was considered a categorical variable. To account for multiple comparisons, we used a Bonferroni correction, and dropped the significance threshold to .0125. Differences between LF and HF rTMS were not hypothesized, but explored where both stimulation conditions were different than sham.

Planned covariates for all analyses included coil-to-cortex distance- given evidence that higher distance may impede the effectiveness of neurostimulation interventions for emotion regulation that are not designed to account for this parameter [77,78] - and data-driven covariates were also examined and added to these analyses as needed. Effect sizes were computed by using Feingold's formula [79] and interpreted using Cohen's specifications [80].

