ID: Pro00103863

Identifying the Optimal Neural Target for Misophonia Interventions

NCT04348591

Study protocol and statistical analysis plan

3/28/2023

Methods:

1. Participants and Procedures

This study was pre-registered under the Clinical Trials ID (NCT04348591) and ran between October 2020 and May 2022. The study was powered based on expected effect size derived from Kumar et al. [2], who compared misophonic participants ($n = 20$) with controls ($n = 22$) to find significant differences in AIC response, with an effect size of 1.27 (mean difference between groups = 2.7 a.u, $SD = 2.11$). For the proposed design, with planned comparisons across condition (downregulate, or listen), sound type (misophonic, aversive, or neutral) and group (misophonic vs. clinical control), and an expected effect size of 1.27, and alpha error rate set at .05, we expected adequate power (over 80%) with 29 participants in each group. Therefore, we aimed to recruit 30 participants in each condition.

Participants were recruited through online websites (e.g., Craigslist, Dukelist), social media (Facebook, Reddit), flyers, and electronic medical record outreach. Participants reached the study predominantly by seeing advertisements on social media and research websites. Many participants who met the severity cutoff for misophonia also found the study via self-guided internet search (see Table 1 for how participants who met the cutoff for each group of interest for the study found the study information).

Table 1. Recruitment methods and success rate in identifying the groups of interest for the study

Recruitment material used	Misophonia participants	Emotion dysregulation participants
Social media (Facebook, Reddit, Instagram)	33.46%	36.42%
Websites (Dukelist, Dukescience, Duke Misophonia website, Dukehealth)	30.08%	28.90%
Word of mouth (friend or medical professional referral)	13.16%	9.83%
Self-guided internet search (including finding the study on clinicaltrials.gov)	12.78%	13.29%
Volunteer registries (BIAC, ResearchMatch, CMER)	6.39%	6.36%
Outreach using electronic medical record	3.38%	4.62%
Newspaper	0.75%	0.58%

Note. Participants were included in the misophonic group if they scored ≥ 2 on the MQ subscales and indicated a severity higher than 6 on the MQ severity scale; participants were included in the emotion dysregulation group if they scored above 89 on the DERS scale.

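### The primary BOLD outcomes are regional, but the only BOLD group test specified is a whole-brain cluster test, so a primary region with no surviving cluster gets no estimate or interval.

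*Combined protocol and SAP*

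**What the plan says.** Section 7 (Statistical Analyses) lists the a priori primary outcomes. Two are imaging outcomes and both are tied to named regions: "BOLD signal differences within the dlPFC and vmPFC during regulation of misophonic versus aversive sounds", and "BOLD signal differences within the AIC when listening to misophonic versus aversive sounds". Whole-brain outcomes are placed among the secondaries, for example "whole-brain BOLD changes when comparing aversive with neutral sound presentation and regulation".

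Section 1 (Participants and Procedures) justifies the sample size from a published comparison of misophonic participants with controls, which is said "to find significant differences in AIC response, with an effect size of 1.27".

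For the group comparison of imaging data, section 7 says that each participant's second-level result "was entered into a third level FSL FEAT analysis assessing the differences between participants" in the two groups. The inference rule follows: "Whole brain Z image statistics (from both functional and PPI analyses) were thresholded using clusters determined by" Z > 2.3 with a corrected cluster significance of .05. Extracted regional values appear once: "correlation analyses with neuroimaging data extracted from regions of interest (ROIs) and baseline behavioral measures were employed".

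**The concern.** The plan itself separates regional BOLD (primary) from whole-brain BOLD (secondary), but it describes a group analysis only at whole-brain level. A thresholded cluster map shows where a difference survives correction. It does not return a group difference for a region with a confidence interval. If no cluster survives in the AIC, the map cannot tell a negligible difference from a moderate one that was poorly estimated.

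At stake is whether the trial can say how large or small its primary imaging differences are. There is also a question of freedom. With no mask, summary measure or multiplicity rule stated for the three regions, those choices stay open after the data are seen, and an a priori primary outcome is meant to prevent that.

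**Working it through.** **1. Outcome against analysis.**

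| Primary outcome (section 7) | Contrast needed | Where the plan names it | Regional group test |
|---|---|---|---|
| dlPFC, regulation | downregulate misophonic − downregulate aversive | in no activation or PPI model | none specified |
| vmPFC, regulation | same | in no model; vmPFC appears only in the outcome list | none specified |
| AIC, listening | listen misophonic − listen aversive | only as a PPI, i.e. connectivity and not activation | none specified |

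The activation contrasts taken to the third level are not listed. The first-level regressors in section 5 (Neuroimaging Data Analysis) include all four conditions needed, so both contrasts can be formed from existing data.

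**2. Could another stated analysis fill the gap?**
- The correlations relate regional values to baseline behavioural measures. They do not estimate a group or sound-type difference.
- The mixed-model and independent t-test sentences in section 7 are generic and name no BOLD outcome.
- The four named neurostimulation models cover SUDS, peak GSR, SCL and HF-HRV. The .0125 threshold is .05/4 and follows those four analyses.
- The only insula mask described (section 5) is an anatomical left insula seed for the PPI. It is not defined as an AIC outcome mask.

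**3. The plan's own sample-size figure.** The stated mean difference and SD give 2.7/2.11 = 1.28, against the stated 1.27. For a plain two-group comparison at d = 1.27 and two-sided .05, 80% power needs 10 per group (normal approximation) or 11 (t-test). At 29 per group, power is 99.7%. So over 80% with 29 is true as a lower bound. The figure of 29 itself does not reproduce from this comparison, and the factorial calculation behind it is not shown. What matters here is that the planning effect is a regional group difference, and that a regional test was feasible under it.

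**4. Precision of a regional comparison.**
- Group sizes, from section 1: 59 were enrolled. In the misophonia group 31% had no current diagnosis (9/29 = 31.0%) and 17.24% had neither a current nor a past one (5/29). Ten percent of controls is 3/30. So the groups are 29 and 30.
- Assumption: all 59 have usable scans; one contrast value per participant per region.
- Half-width in SD units = t(.975, 57) × √(1/29 + 1/30) = 2.002 × 0.2604 = **0.52**.
- With the quantile for .05/3: 2.467 × 0.2604 = 0.64.
- With only the 27 per group who attended the neurostimulation day, the 95% half-width is about 0.55.

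**5. Multiplicity.** Three independent tests at .05 without correction have a familywise error of 1 − 0.95³ = 14.3%.

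**The case against.** **The search volume covers these regions.** A whole-brain third-level test includes dlPFC, vmPFC and AIC, so a surviving cluster in one of them could be reported. Whole-brain cluster correction is also an accepted method. This stands. It limits the concern to the missing estimate and interval, above all where no cluster survives.

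**A reader might infer that the plan answers its secondary imaging question instead of its primary one.** The text does not support that. The listed whole-brain secondaries use different contrasts (aversive or misophonic against neutral sounds), whereas the primaries compare misophonic with aversive sounds.

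**A reader might also infer that the whole-brain test gives up power.** The documents cannot show this. Cluster-test power depends on smoothness, cluster extent and region size, and these do not determine it from what is given. A rough comparison does not favour the regional test either. At 29 and 30, a single voxel passes Z > 2.3 with probability 50%, 78% and 99.5% at d = 0.6, 0.8 and 1.27. A regional test at .05/3 has power 44%, 73% and 99.1%. The values 0.6 and 0.8 are illustrative, and a voxel pass rate is not the power of a cluster test. No power argument is made here.

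**Regional tests may exist elsewhere.** Section 5 says the complete fMRI analyses will be presented separately, and the generic t-test sentence sits beside the mention of extracted regional values. Both are fair. They show that regional tests are possible, but this document, which serves as the SAP, does not specify them.

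**The estimand could be read differently.** The outcome wording names a difference between sound types, not between groups. The group reading comes from the sample-size basis and the third-level group analysis. The plan should say which is meant.

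**Conclusion.** The concern holds as a mismatch between primary outcome and specified analysis. For three a priori regional outcomes, the plan gives no mask, regional summary, regional group model, interval or multiplicity rule. One of the two contrasts needed appears in no model and the other only as connectivity. Followed as written, the plan cannot state the size of a primary difference in any region without a surviving cluster.

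A direct regional comparison would bound each difference to about ±0.52 SD (95%), assuming 29 and 30 analysable participants and a between-group estimand. The conclusion does not rest on the whole-brain test being weaker, or on a claim that regional analyses were never done. It concerns what this document specifies. The change should be made, but it does not call the imaging data into question.

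**What to change.** Add a regional analysis for the imaging primaries to section 7:

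- **Measure.** Each participant's mean contrast value in the region: downregulate misophonic minus downregulate aversive for dlPFC and vmPFC; listen misophonic minus listen aversive for AIC.
- **Masks.** Anatomical or published, chosen without reference to the group results. They must be independent of the individual stimulation targets, because section 5 picks those targets as the strongest z-values in the same scans.
- **Model.** A linear model comparing groups, reporting the difference with its 95% CI for every region, whether or not a cluster survives.
- **Multiplicity.** A stated correction over the three regions.
- **Whole-brain maps.** Keep them as a complementary analysis.
- **Status.** The study ran to May 2022 and the document is dated March 2023. If the masks were not fixed before the data were seen, label the regional analysis post hoc.

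The cost is SAP wording, three masks and three group comparisons on existing scans. The downside is that masks must be chosen and justified, and averaging over a large mask can dilute a focal effect.
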